## List of Abbreviations

ADCC	Antibody-dependent cell-mediated cytotoxicity
AE	Adverse event
AH	Antihistamine
BP	Blood pressure
CFR	Code of Federal Regulations
CholU	Cholinergic Urticaria
CINDU	Chronic Inducible Urticaria
CIU	Chronic Idiopathic Urticaria
CRF	Case Report/Record Form
CSU	Chronic Spontaneous Urticaria
CTCAE	Common Terminology Criteria for Adverse Events
CU	Chronic Urticaria
ECG	Electrocardiogram
ET	Early Termination
FSH	Follicle-stimulating hormone
GCP	Good Clinical Practice
HbsAg	Hepatitis B surface antigen
HIPAA	Health Information Portability and Accountability Act
HIV	Human Immunodeficiency Virus
IB	Investigator Brochure
ICF	Informed Consent Form
ICH	International Conference on Harmonization
IEC	Independent Ethics Committee
IgE	Immunoglobulin E
IRB	Institutional Review Board
IRR	Infusion-Related Reaction(s)
IV	intravenous administration
MC	Mast cell

MCID	Minimal Clinical Importance Difference
MedDRA	Medical dictionary for regulatory activities
NaCl	Sodium chloride
NCI	National Cancer Institute
NOAEL	No-observed-adverse-effect level
PCE	Pulse-Controlled Ergometry Test
PID	Patient Identification Number
PP	Per-Protocol population
PT	Preferred Term
QOD	Every other day
QoL	Quality of Life
RBC	Red blood cell(s)
SAE	Serious adverse event
SAP	Statistical analysis plan
SC	subcutaneous administration
SOC	System Organ Classification
TEAE	Treatment-Emergent Adverse Event
TESAE	Treatment-Emergent Serious Adverse Event
UAS	Urticaria Activity Score
UAS7	Weekly Urticaria Activity Score
UCT	Urticaria control test
UF	Urticaria factitia
UPDD	Urticaria Patient Daily Diary
VAS	Visual Analog Scale
WBC	White blood cells(s)
WHO	World Health Organization

## 1. Protocol Synopsis

Study Title	An Open-Label, Pilot Study to Assess the Efficacy and Safety of AK002 (Siglec-8) in Subjects with Antihistamine-Resistant Chronic Urticaria
Short Title	CURSIG (Chronic Urticaria Response to AK002 (Siglec-8))
Rationale	
Chronic urticaria (CU) is a skin condition, which is characterized by transient pruritic wheal-and-flare-type skin reactions and, in some subjects, the occurrence of angioedema. About 1% of the population in Europe has chronic or recurrent urticaria (Hellgren, 1972). Subjects with CU are often impaired in their quality of life, with negative effects on sleep, daily activities, school/work life, and social interactions.
 
Therefore, the current guidelines of the European Academy of Allergy and Clinical Immunology (EAACI)/Global Allergy and Asthma European Network (GALEN)/European Dermatology Forum (EDF)/World Allergy Organization (WAO) state that the aim of treatment for all types of urticaria is to achieve complete symptom relief.
 
The current treatment guidelines for the management of all forms of urticaria recommend the use of non-sedating oral H1-antihistamines as first-line therapy. In more than 50% of subjects, symptoms persist with standard dosing of antihistamines. In antihistamine-refractory subjects with chronic spontaneous urticaria (CSU), the only currently licensed treatment is omalizumab, a monoclonal anti-IgE antibody. In subjects with chronic inducible urticaria (CINDU) including cholinergic urticaria (CholU) and urticaria factitia (UF), no other licensed drugs are available, and subjects often need to be treated with omalizumab, cyclosporin, or other off-label drugs.
 
In double-blind placebo-controlled studies in selected antihistamine-refractory subjects, omalizumab has been shown to be very effective in the treatment of CSU and is recommended as third-line therapy if symptoms persist with 4-fold antihistamines. However, some CSU subjects continue to have symptoms despite omalizumab treatment or do not respond at all to omalizumab treatment. Approximately 60–65% of omalizumab patients continue to experience symptoms despite treatment, so there clearly is a need for new and better treatments (Saini, 2015). Furthermore, omalizumab is not licensed for the treatment of CINDU. There is a significant unmet need for new targeted therapeutic options for subjects with CSU and CINDU.

Study Design/Phase	This is an open-label, proof-of-concept study.
Objectives	To assess the effects of AK002 on symptom control in subjects with chronic urticaria. CU subjects will document triggers and symptoms (wheals, pruritus, etc.), as well as quality of life (QoL), before, during and after treatment. Subjects will also be subjected to standardized provocation tests and assessment of symptom development.

Primary Objective	To assess the efficacy of AK002 on symptoms in subjects with CU (change in urticaria control test [UCT] score).
Secondary Objectives	The efficacy, safety and pharmacodynamics of AK002 on urticaria symptoms, QoL, provocation testing, and histological criteria.
	The effects of AK002 in CU subjects will be assessed through the following evaluations:
	1) Safety and tolerability (adverse events, laboratory safety tests etc.)
	2) Disease activity scores (UAS7, [REDACTED])
	3) [REDACTED]
	4) Number of symptom-free days
	5) Use of rescue medication (up to 3 sgAH tablets/day)
	6) Effects on [REDACTED]
	7) Number of [REDACTED]
	8) [REDACTED]
	9) Changes in trigger thresholds (in CINDU, including CholU)
	10) Rate of [REDACTED] (UCT, [REDACTED])
	11) Serum levels of potential biomarkers of disease activity and treatment responses
	12) Rates of relapse and sustained response during the follow-up period
Endpoints	
Primary Endpoint	The primary endpoint is the change in Urticaria Control Test (UCT), a score for symptom control in chronic urticaria, from baseline to Week 22 in CU subjects after treatment with AK002. A change of the UCT score of 3 or more points is regarded as clinically relevant (minimal clinically important difference [MCID]).
Other Endpoints	
 
1) Safety of subjects treated with AK002: This includes physical examination, routine safety laboratory assessments, vital signs, electrocardiogram (ECG), urine safety, and adverse event reporting (Visits 2–10)
 
2) Change in disease activity as assessed by UAS7 and/or [REDACTED] from Baseline to Visits 3, 5, 8, and 10
 
3) Change in number of symptom-free days per week (patient diary-based CSU score; wheals, flares, itch, avoidance behavior) from Baseline to Visits 3, 5, 8, and 10
 

Other Endpoints cont.	
4) Change in [REDACTED] assessed by [REDACTED] from Baseline to Visits 3, 5, 8, and 10
 
5) Change in number of intake of rescue medication from Baseline to Visits 3, 5, 8, and 10
 
6) In case of [REDACTED], change in [REDACTED] from Visit 2 to Visits 3, 5, 8, and 10, as assessed by [REDACTED]
 
7) Change in number of [REDACTED] from Baseline to Visits 3, 5, 8, and 10
 
8) Change in [REDACTED] from Baseline (Day 1) to Visits 3, 5, 8, and 10
 
9) Changes in trigger threshold from Baseline (Day 1) to Visits 3, 5, 8, and 10, as assessed by Pulse Controlled Ergometry Test (PCE) FricTest®, as applicable
 
10) Rates of complete response, partial response, and non-response based on UCT, [REDACTED], trigger thresholds (where applicable), and QoL from Baseline to Visits 3, 5, 8, and 10
 
11) Serum levels at baseline (Day 1) and change from Baseline to Visits 3, 5, 8, and 10 of serum levels of potential biomarkers in AK002-treated subjects (e.g., tryptase, eosinophils, total IgE, basophils, eosinophil cationic protein)
 
12) Rates of AK002-treated subjects with relapse, rebound, sustained treatment effects at Visit 7

Study Drug	AK002 (Siglec-8 inhibitor)
Dose and Route of Administration	
Up to 6 doses of AK002 will be given over the course of the study. AK002 will be administered as an intravenous (IV) infusion at a dose of 0.3 mg/kg given over a period of approximately 4 hours on study Day 1 (Dose 1). If well tolerated, dose will be increased to 1 mg/kg, given over a period of 4 hours on study Day 29 (Dose 2) and Day 57 (Dose 3) (<math>\pm</math>2 days). For Doses 4, 5, and 6 on Day 85, Day 113, and Day 141, respectively, dose will be increased to 3 mg/kg if patient has UCT score of <math><12</math>, and/ or at the discretion of the Investigator in consultation with the Allakos Medical Monitor. If the UCT score <math>\geq 12</math> and if the Investigator in consultation with the medical monitor feels that the patient has received adequate symptom improvement, then the patient will continue to receive 1 mg/kg dose.
 
Subjects in the CholU, UF, and CSU-XOLAIR® (omalizumab) failure cohorts who received all 6 infusions of AK002, were followed at least through Day 155, and demonstrated severe symptoms of urticaria following the last dose of treatment will be allowed the option to receive extended dosing with up to 12 additional doses of AK002 (see Appendix 2). They will have to be treated with extended dosing within 6 months of last dose.

Dose and Route of Administration cont.	
All subjects that decide to receive extended dosing will start with a dose of 0.3 mg/kg, followed by possible dose increases to 1 mg/kg and 3 mg/kg for subsequent infusions.
 
The Investigator in consultation with the Medical Monitor may increase the dose to 6 mg/kg and then to 10 mg/kg if they think that the patient has not received benefit from the lower doses.
 
The amount of AK002 to be administered will be calculated based on the patient's body weight determined within 24 hours of each infusion. The calculated amount of AK002 (████████) based on body weight will be diluted with 0.9% NaCl for IV injection. Final combined volume of each IV bag of AK002 + 0.9% NaCl will be 120 mL.
 
Note: Exactly 100 mL of the calculated dose of AK002 will be administered to each patient. The extra 20 mL is to be used to prime the IV infusion line during the preparation of the IV line at the bed side.
 
It is recommended that each dose of 120 mL is prepared in an empty medication delivery bag. The doses for the extension study are outlined in Appendix 2.

Centers/Countries	Approximately 4 study centers in the USA and Germany. Only the sites in Germany will participate in the extension study.
Number of Subjects	
N (total) = Approximately 48 subjects with chronic urticaria
 
This will include the following cohorts:
 
 
• Approximately 12 subjects with Cholinergic urticaria (CholU)
 
• Approximately 12 subjects with Urticaria factitia (UF)
 
• Approximately 12 XOLAIR® (omalizumab) naïve subjects with Chronic spontaneous urticaria (CSU)
 
• Approximately 12 subjects with Chronic spontaneous urticaria (CSU) who did not achieve an adequate response on XOLAIR® (omalizumab) in the opinion of the Investigator
 
 
The extended dosing will be applicable only to the subjects in the CholU, UF, and CSU-XOLAIR® (omalizumab) failure cohorts.

Rationale for Sample Size	The planned sample size of approximately 48 subjects is based on common practice in early phase, proof-of-concept studies.
Duration of Patient Participation and Duration of Study	
The total study duration for each patient will be approximately 32 weeks. This includes:
 
 
• A screening period of 4 weeks prior to study drug administration
 
• Administration of study drug at Day 1, Day 29, Day 57, Day 85, Day 113, and Day 141
 
• Follow-up through Day 197 (8 weeks post last dose)
 

Duration of Patient Participation and Study cont.	Subjects who elect to receive optional extended dosing with up to 12 additional doses of AK002 will participate for up to an additional 12 months (see Appendix 2 ).
Inclusion Criteria	
1) Adults (<math>\geq 18</math> and <math>\leq 85</math> years old)
 
2) Body weight <math><125</math> Kg
 
3) Informed consent signed and dated
 
4) Able to read, understand, and willing to sign the informed consent form and comply with study procedures
 
5) Diagnosis of CU for at least 3 months, refractory to antihistamine treatment in single or 4-fold dosage.
 
6) Willing, committed, and able to return for all clinic visits and complete all study-related procedures, including willingness to have IV infusion of study drug administered by a qualified person
 
7) Females of childbearing potential must have a negative pregnancy test at Baseline. Female subjects must be willing to use highly effective contraception (Pearl-4 Index <math><1</math>) or abstain from sexual activity from Screening until the end of the study, or for 120 days following the last dose of study drug, whichever is longer. A woman will be considered not of childbearing potential if she is post-menopausal for greater than two years (FSH <math>>40</math> mL) or surgically sterile (bilateral tubal ligation, bilateral oophorectomy, or hysterectomy). Male patients with female partners of childbearing potential must agree to use a highly effective method of contraception from Screening until the end of the study or for 120 days following the last dose of study drug, whichever is longer. All fertile men with female partners of childbearing potential should be instructed to contact the Investigator immediately if they suspect their partner might be pregnant (e.g., missed or late menstrual period) at any time during study participation.
 
8) No participation in other clinical trials 4 weeks before participation in this study
 
9) Uncontrolled CU (UCT <math><12</math>) at the time of enrollment
 
10) For extended dosing, subjects must have a baseline (Day 1) UCT of <math>\leq 5</math> and a week 22 (Day 155) UCT of <math>\geq 12</math> (Complete Response). They must have a UCT of <math>\leq 5</math> post-week 22 (Day 155) and by week 44 (Day 309) i.e., within 6 months from last dose

Exclusion Criteria	
1) Acute urticaria
 
2) Concurrent/ongoing treatment with immunosuppressives (e.g., cyclosporine, methotrexate, dapsone, or others) within 4 weeks or 5 half-lives prior to Baseline, whichever is longer

Exclusion Criteria cont.	

3) Significant medical condition rendering the patient immunocompromised or not suitable for a clinical trial

4) Significant concomitant illness that would adversely affect the subject's participation or evaluation in this study

5) History of malignancies within five years prior to screening other than a successfully treated non-metastatic cutaneous, basal, or squamous cell carcinoma and/or in situ cancer

6) Presence of clinically significant laboratory abnormalities

7) Lactating women or pregnant women

8) Substance abuse (drug or alcohol) or any other factor (e.g., serious psychiatric condition) within the last 5 years that could limit the subject's ability to comply with study procedures

9) Subjects who are detained officially or legally to an official institute or those that have been committed to an institution by virtue of an order issued either by the judicial or the administrative authorities will be excluded from the study

10) Use of omalizumab within the last 2 months

11) Receipt of intravenous IgG therapy 30 days prior to Baseline

12) Plasmapheresis 30 days prior to Baseline

13) Use (daily or every other day) of Doxepin 14 days prior to Baseline

14) Receipt of inactive vaccination or live attenuated vaccine 30 days prior to Baseline

15) Use of H2-antihistamines 7 days before Baseline

16) Intake of leukotriene antagonists within 7 days prior to enrollment

17) Intake of systemic corticosteroids (e.g., oral or depot) within 14 days prior to enrollment

18) Positive screening for ova and parasite test at Baseline

19) Treatment of helminthic parasite within 6 months of screening

20) Positive HIV serology at screening

21) Positive Hepatitis serology at baseline, except for vaccinated patients or patients with past but resolved hepatitis at screening

22) Donation or loss of >500 mL of blood within 56 days prior to administration of study drug or donation of plasma within 7 days prior to administration of drug

23) Known hypersensitivity to any ingredients of AK002 or drugs related to AK002 (e.g., monoclonal antibodies, polyclonal gamma globulin)

---------------------------------	---

Concomitant Medications	Second-generation H1-antihistamines as concomitant medication once daily and up to 4 times daily on demand (drug intake to be documented in the patient diary).
Safety Evaluations	
Safety and tolerability will be assessed throughout the study by monitoring and evaluating adverse events (AEs), including any complications resulting from the IV infusion. All treatment-emergent adverse events (TEAEs) will be collected from the start of study drug administration through 8 weeks after last dose received or Early Termination (ET). Severity will be assessed using the National Cancer Institute (NCI) Common Terminology Criteria for Adverse Events (CTCAE) Version 4.03. All AEs will be assigned a severity grade and relationship to study drug.
 
Additional safety evaluations include clinical laboratory tests, including anti-drug antibody to AK002, complete blood counts, chemistries, and urinalyses, ECGs; and vital signs.

Statistical Methodology	All subjects who received a dose of study drug will be included in the analysis. All safety data will be listed. Where appropriate, summary statistics will be provided (number of non-missing values, mean, median, standard deviation, minimum, and maximum for continuous variables, and number and percentage for categorical variables) for all measures, including demographic and baseline values, clinical scores and safety endpoints.
Rationale for Amendment 4.1	
The following modifications have been incorporated into Amendment 4.1 of the protocol.
 
 
• Procedures that allow subjects in the CholU, UF, and CSU-XOLAIR® (omalizumab) failure cohorts who received all 6 infusions of AK002, were followed through Day 155, and demonstrated severe symptoms of urticaria following discontinuation of treatment, to be offered the option to receive extended dosing with up to 12 additional doses of AK002. Offering extended dosing allows subjects with no other treatment options continued access to AK002 and the benefit obtained during the initial 6 infusions. It also allows for collection of longer-term efficacy, safety, and tolerability data of AK002.
 
• PK will be analyzed retroactively using backup blood samples.
 

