### **8.3.4 Preparation of Study Drug**

Please refer to the Pharmacy Manual for additional details regarding study drug preparation.

The amount of AK002 to be administered will be calculated based on the patient's body weight determined within 24 hours of each infusion.

The calculated amount of study drug based on body weight will be diluted with 0.9% NaCl for IV injection.

The final combined volume of the IV bag of study drug + 0.9% NaCl will be **120 mL**.

**Note:** Exactly **100 mL** of the calculated dose of study drug will be administered to the patient. The extra 20 mL is to be used to prime the IV infusion line during the preparation of the IV line at the bed side.

It is recommended that each dose of 120 mL is prepared in an empty medication delivery bag.

For all 6 doses (0.3 mg/kg on Day 1, 1 mg/kg on Day 29 and Day 57, and 3 mg/kg on Day 85, Day 113, and Day 141), 100 mL dose of study drug will be infused over approximately 4 hours.

After each dose, the patient will be monitored for at least 4 hours after IV administration. At the discretion of the PI, monitoring may be extended for an additional 24 hours.

Detailed instructions for preparing the drug are in the Pharmacy Manual.

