### 8.3.5 AK002 Administration

Premedication with oral doses of acetaminophen/paracetamol (1000 mg) and cetirizine (10 mg) will be given 1 hour prior to the infusion for doses 1 and 2. Any premedication for subsequent doses will be based on the Investigator's discretion. AK002 will be infused through a peripheral vein IV set. The IV line will be kept open before and after the infusion with sufficient quantities of 0.9% NaCl to assure patency.

Based on the patient's weight, the designated clinical staff will prepare the appropriate dilution of AK002 at 0.3 mg/kg (for Day 1), 1 mg/kg (for Day 29 and Day 57), and 3 mg/kg (for Day 85, Day 113, and Day 141) for IV administration. Appropriate aseptic technique will be used, and the study drug will be prepared according to the Pharmacy Manual for AK002.

The site's designated clinical staff will keep accurate and current accounting of the preparation and dose calculation of study drug for each patient, with source, quantities of study medication dispensed, used, and returned. All dosage calculations will be documented on the source documents. A study drug receipt, dispensation, and disposition log will be maintained by the pharmacist on the Investigational Drug Accountability Record. A study monitor will verify entries on these documents throughout the course of the study.

Specific instructions on administration are detailed in the Pharmacy Manual. In general, all doses i.e., 0.3 mg/ kg at Day 1, 1 mg/kg at Day 29 and Day 57, and either 1 mg/kg or 3 mg/kg (depending on UCT score) at Day 85, Day 113, and Day 141 will be given as an IV infusion over approximately 4 hours, following an observation period of 4 hours.

All dosages prescribed and dispensed to the patient and all dose changes during the study must be recorded on the appropriate eCRF.

Subjects in the CholU, UF, and CSU-XOLAIR® (omalizumab) failure cohorts who received all 6 infusions of AK002, were followed through Day 155, and demonstrated severe symptoms of urticaria following discontinuation of treatment will be eligible to receive extended dosing with up to 12 additional doses of AK002 (see [Appendix 2](#)).

For extended dosing, subjects must have a baseline (Day 1) UCT of  $\leq 5$  and a week 22 (Day 155) UCT of  $\geq 12$  (Complete Response). They must have a UCT of  $\leq 5$  between Day 155 and Day 309 (i.e., within 6 months from last dose).

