11.1 Appendix A: Exclusion Criteria for the Per Protocol Populations

The following criteria will be used to further exclude subjects from the PP population:

- Subject received incomplete dose of study drug.
- Subject received prohibited medication that could potentially confound the efficacy outcome.

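### The protocol does not say whether the weight-based amount of AK002 fills the 120 mL bag or the 100 mL infused; read literally, 83.3% of each stated mg/kg dose is delivered

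*Protocol*

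**What the plan says.** Protocol Section 8.3.4, which has no blacked-out text, sets out the preparation in steps, and the synopsis (Dose and Route of Administration) repeats them:

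- The amount is weight-based: "The amount of AK002 to be administered will be calculated based on the patient's body weight determined within 24 hours of each infusion".
- That amount goes into the bag: "The calculated amount of study drug based on body weight will be diluted with 0.9% NaCl for IV injection".
- The bag volume is fixed: "Final combined volume of each IV bag of AK002 + 0.9% NaCl will be 120 mL".
- Part of the bag is infused: "Exactly 100 mL of the calculated dose of AK002 will be administered to each patient".
- The rest has another use: "The extra 20 mL is to be used to prime the IV infusion line during the preparation of the IV line at the bed side".

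Section 8.3.4 attaches the word dose to both volumes. One sentence reads "It is recommended that each dose of 120 mL is prepared in an empty medication delivery bag"; a later one calls the 100 mL that is infused the dose, for all six infusions.

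On line handling, Section 8.3.5 says: "The IV line will be kept open before and after the infusion with sufficient quantities of 0.9% NaCl to assure patency". No saline volume is given. Appendix 2 (Procedures) carries dose preparation over to extended dosing unless stated otherwise.

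In the SAP, Section 7.6.1 summarises exposure by duration in days and by number of doses received. Appendix A (Section 11.1) excludes a subject from the per-protocol population under this criterion: "Subject received incomplete dose of study drug".

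**The concern.** If the amount meant for the patient is spread through 120 mL, infusing 100 mL cannot deliver all of it. If the 100 mL does contain the full amount, the bag must have been made up with 1.2 times that amount, which no visible passage says. The two descriptions cannot both be true.

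What is at stake is the meaning of the dose labels. Infusion reactions, eosinophil counts, AK002 concentrations and UCT changes will be read against 0.3, 1 and 3 mg/kg, and against 6 and 10 mg/kg in the extension. A follow-on study would build on those labels.

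The planned data would not expose the problem. SAP 7.6.1 does not use mg. Protocol 8.3.6 and 8.3.8 ask for infusion times and interruptions, and 8.3.5 for dosages prescribed and dispensed. No visible section asks for the volume infused or the mg delivered. The Appendix A exclusion gives no reference (100 mL, 120 mL or full mg) against which a dose would be incomplete.

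**Working it through.** **Inputs.** Bag 120 mL, infused 100 mL, priming 20 mL (synopsis and 8.3.4). Dose levels 0.3, 1 and 3 mg/kg in the main study, 6 and 10 mg/kg as possible increases in extended dosing (synopsis, 8.3.4, Appendix 2). Uniform mixing of the bag is assumed.

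**The protocol's own figure.** 100 + 20 = 120 mL. The volumes balance; the protocol states no delivered fraction.

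**Formula.** Delivered fraction = (mg in bag ÷ calculated mg) × (mL of bag solution reaching the patient ÷ 120).

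**Reading A: the bag holds exactly the calculated amount and 100 mL reaches the patient.** 1 × 100/120 = 0.833, with 20/120 = 16.7% in the priming volume.

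| Stated mg/kg | × 100/120 |
|---|---|
| 0.3 | 0.25 |
| 1 | 0.83 |
| 3 | 2.5 |
| 6 | 5.0 |
| 10 | 8.3 |

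Cumulative main-study dose:

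- 3 mg/kg at Doses 4 to 6: 0.3 + 1 + 1 + 3 + 3 + 3 = 11.3; 11.3 × 100/120 = 9.4 mg/kg.
- 1 mg/kg at Doses 4 to 6: 0.3 + 5 × 1 = 5.3; 5.3 × 100/120 = 4.4 mg/kg.

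**Reading B: the 100 mL holds the calculated amount.** The bag must hold 120/100 = 1.2 times that amount. Then 1.2 × 100/120 = 1.00.

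**Reading A with flushing.** Suppose the saline given afterwards returns r mL of the priming volume to the patient. The fraction is (100 + r)/120. The documents give no value for r, so the range 0 to 20 mL is an assumption.

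| r (mL) | Delivered |
|---|---|
| 0 | 83.3% |
| 5 | 87.5% |
| 10 | 91.7% |
| 15 | 95.8% |
| 20 | 100% |

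Any r above zero conflicts with the instruction to give exactly 100 mL.

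**Result.** These readings span 83.3% to 100% of the stated dose, and no visible passage chooses among them.

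**The case against.** The strongest reply is that the 20 mL is ordinary overfill. The synopsis and 8.3.4 describe the 100 mL as the calculated dose and the 20 mL as extra, which fits a bag made up so that 100 mL delivers the label dose. The deciding rule may also lie in text not available here. Sections 8.3.2, 8.3.4 and 8.3.5 refer to the Pharmacy Manual. A parenthesis directly after the calculated amount is blacked out in the synopsis, as is a value for dose preparation in 8.3.2. This stands in part: it prevents 83.3% from being asserted as the delivered dose. It does not remove the contradiction, because 8.3.4 gives the steps without any visible gap or overage. If the Manual contains an overage, the protocol's description is incomplete; if it does not, the labels overstate the delivered dose unless all of the priming volume is flushed in.

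A second reply is that little in the analysis depends on this. The study has one arm and no hypothesis tests (SAP 3.5), and efficacy is summarised by cohort and visit. A uniform factor would leave the UCT change and its confidence interval as they are. That is correct; the consequence is for dose labels and what is built on them.

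A third is that the mg prepared can be recovered, since dosage calculations are kept in source documents (8.3.5, 8.3.7) and altered administrations are recorded (8.3.6). That covers the amount in the bag, but not the volume that reached the patient. AK002 concentrations (SAP 7.9) are not a dependable substitute: protocol 10.5.7.4 plans them retroactively, if possible, from backup samples.

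**Conclusion.** The preparation text contradicts itself about the delivered dose. On the literal reading, with no overage and no flush, delivery is 83.3% of every stated dose, and 9.4 instead of 11.3 mg/kg cumulatively if 3 mg/kg is given at Doses 4 to 6. If the bag holds 1.2 times the calculated amount, delivery is 100%. Without overage but with some return of priming volume, it lies between the two. All figures assume a uniformly mixed bag.

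Four stronger conclusions might be inferred, and the documents support none of them:

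- That every patient in fact receives 83.3%. The overfill wording, the Pharmacy Manual and the blacked-out text leave this open.
- That delivery could exceed the stated dose. This needs an overage and more than 100 mL reaching the patient, against the instruction to give exactly 100 mL.
- That dose differs between Germany and the US. SAP 6.7 compares response rates between the countries, but nothing shows that sites prepare bags differently.
- That the per-protocol exclusion would remove everyone. The planned infusion is 100 mL, and an incomplete dose reads naturally as an infusion stopped under 8.3.6. The defect is only that the criterion has no stated reference.

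**What to change.** 1. Reconcile the synopsis, Sections 8.3.4 and 8.3.5 and the Pharmacy Manual. State whether the weight-based amount is contained in the 120 mL bag or in the 100 mL infused, and how drug left in the line is treated. Correct whichever statement is untrue. Which amount is right is for the sponsor to establish.
2. Record, for each infusion, the mg in the bag and the volume of bag solution that reached the patient, including any line volume flushed in.
3. In SAP 7.6.1, add mg delivered = mg in bag × (mL infused + mL flushed from the line) ÷ 120, and the same figure per kg. The flushed volume must be counted or the formula understates delivery.
4. If bags had no overage, correct the dose labels in the study report to the delivered amounts.
5. In SAP Appendix A, define an incomplete dose against the intended infused volume.

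The cost is clarifying text in the protocol, Pharmacy Manual and SAP, one derived exposure variable, and a data item for delivered volume that no visible section now requires. For infusions already given, mg in the bag should be recoverable from source; the volume delivered may not be, and the report should then give a range. Reported doses may turn out up to 16.7% lower.
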